5. INTERIM ANALYSES

No interim analyses are planned in this trial.

An independent Data and Safety Monitoring Board (DSMB) will safeguard the interests of adolescent subjects by assessing the safety of the intervention. The DSMB will review safety data on a regular basis as set out in a DSMB charter. The data for review will be outlined in a DSMB charter. The DSMB will have access to individual treatment codes and will be able to merge these with the collected study data whilst the study is ongoing. For reference, the DSMB will also have access to study data from adults.

The personnel involved in the clinical study at AstraZeneca will remain blinded to these analyses and will have no knowledge of the results presented to the DSMB.

6. CHANGES OF ANALYSIS FROM PROTOCOL

The protocol specifies that in general the last measurement on or prior to the date of randomisation will serve as the baseline measurement. This is clarified in [Section 3.1.1](#) as being with reference to the date of randomisation for efficacy variables, but date of first dose of IP with reference to safety variables (should a situation exist for any subject in which these two dates are different).

The protocol specifies that one of the exploratory objectives is to explore the effect of 210 mg tezepelumab SC Q4W on total immunoglobulin levels. Total serum IgE is included in [Section 1.1.3](#), Other Secondary Objectives: To assess the effect of 210 mg tezepelumab SC Q4W on biomarkers, so removed from [Section 1.1.5](#).

The protocol defines an emergency room or urgent care visit due to asthma that requires systemic corticosteroids, as one of 3 criteria for a protocol defined exacerbation. However, only information on emergency room visits and use of systemic corticosteroids are collected

in the eCRF. The text in [Section 1.1.3](#), [Section 3.2.3.1](#), [Section 3.2.3.3](#), [Section 3.2.4.1](#), [Section 4.2.4.4](#) and [Section 4.2.6](#) has been updated to reflect this.

The number of asthma symptomatic days has been included as an exploratory endpoint in [Section 3.2.3.5](#), but is not included as an exploratory endpoint in the protocol.

The total daily asthma symptom scores, derived from the Global Asthma Symptom items assessment used for the alerts system, has been included as an exploratory endpoint in [Section 3.2.4.3](#), but is not included as an exploratory endpoint in the protocol. The daytime and night-time scores from this assessment have also been included.

The protocol specifies that serum trough concentrations will be the endpoint used to evaluate the pharmacokinetics (PK) and immunogenicity of tezepelumab; we will include data from follow-up visits where appropriate, so the word 'trough' has been removed from [Section 1.1.3](#).

8. APPENDIX

8.1 Adverse events of special interest

8.1.1 Anaphylactic reactions

Potential anaphylactic reactions will be defined on the basis of Sampson's criteria (see [Sampson et al., 2006](#)). These will be identified using a modified Standardized MedDRA Query (SMQ), with additional constraints on the timing of the AE onset date relative to the timing of the injection.

Confirmed anaphylactic reactions will be those defined following medical review of the preferred terms identified as potential anaphylactic reactions, as well as any relevant supporting data.

AESIs and related definitions based on MedDRA terms are not included in this SAP to facilitate their maintenance (e.g. management of MedDRA version changes), and for convenience in using them directly in SAS programming. These detailed definitions will be finalised by the study team prior to the primary database lock and provided together with the study datasets at the time of submission.

8.1.2 Immune complex disease (Type III hypersensitivity reactions)

Immune complex disease will be defined using a single PT of "Type III immune complex mediated reaction". Since this will already be covered by the general AE reporting by SOC/PT, separate summary tables will not be needed for this AESI.

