8.3.6 Adverse events based on signs and symptoms

All AEs spontaneously reported by the subject or reported in response to the open question from the study site staff: **Have you/the child had any health problems since the previous visit/you were last asked?** or revealed by observation will be collected and recorded in the CRF. When collecting AEs, the recording of diagnoses is preferred (when possible) to recording a list of signs and symptoms. However, if a diagnosis is known and there are other signs or symptoms

that are not generally part of the diagnosis, the diagnosis and each sign or symptom will be recorded separately.

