8.3.8 Adverse Events of Special Interest

An adverse event of special interest (AESI) is an event of scientific and medical interest towards improving the understanding of the IP. An AESI may be serious or non-serious. For this study, AESIs include:

- Anaphylactic reactions
- Immune complex disease (Type III hypersensitivity reactions)
- Malignancy
- Helminth infections
- Severe infections which are defined as:

- SAEs or
- Requiring treatment with systemic antiviral medications, intravenous antibiotics or medications for helminth parasitic infection or
- Requiring a permanent discontinuation of study drug
- Injection site reactions
- Opportunistic infections
- Guillain Barre Syndrome

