Appendix G Anaphylaxis: signs and symptoms, management

G 1 Introduction

As with any antibody, allergic reactions to dose administration are possible. The World Health Organization has categorized anaphylaxis into 2 subgroups, which are clinically indistinguishable: immunologic [IgE-mediated and non-IgE-mediated (eg, IgG and immune complex mediated) and nonimmunologic (Johansson et al, 2004)]. The clinical criteria for defining anaphylaxis for this study are listed in section 2. A guide to the signs and symptoms and management of acute anaphylaxis is provided in section 3. Appropriate drugs, such as epinephrine, antihistamines, corticosteroids, etc, and medical equipment to treat anaphylactic reactions must be immediately available at study sites, and study personnel should be trained to recognize and treat anaphylaxis according to local guidelines.

If an anaphylactic reaction occurs, a blood sample will be drawn from the subject as soon as possible after the event, at 60 minutes \pm 30 minutes after the event, and at discharge for analysis of serum tryptase.

G 2 Clinical Criteria for Defining Anaphylaxis and Immune Complex Disease

Anaphylaxis

In adults, anaphylaxis is highly likely when any one of the following 3 criteria is fulfilled:

1. Acute onset of an illness (minutes to several hours) with involvement of the skin, mucosal tissue, or both (eg, generalized hives, pruritus or flushing, swollen lips-tongue-uvula)
AND AT LEAST ONE OF THE FOLLOWING
 - (a) Respiratory compromise (eg, dyspnea, wheeze-bronchospasm, stridor, reduced PEF, hypoxemia).
 - (b) Reduced blood pressure (BP) or associated symptoms of end-organ dysfunction (eg, hypotonia [collapse], syncope, incontinence).
2. Two or more of the following that occur rapidly after exposure to a likely allergen for that subject (minutes to several hours):
 - (a) Involvement of the skin-mucosal tissue (eg, generalized hives, itch-flush, swollen lips-tongue-uvula).
 - (b) Respiratory compromise (eg, dyspnea, wheeze-bronchospasm, stridor, reduced PEF, hypoxemia).
 - (c) Reduced BP or associated symptoms (eg, hypotonia [collapse], syncope, incontinence).
 - (d) Persistent gastrointestinal symptoms (eg, crampy abdominal pain, vomiting).

3. Reduced BP after exposure to known allergen for that subject (minutes to several hours):
Adults: systolic BP of less than 90 mm Hg or greater than 30% decrease from that subject's baseline.

Immune Complex Disease

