Immune complex disease or Hypersensitivity Type III is evoked by the deposition of antigen-antibody or antigen-antibody-complement complexes on cell surfaces, with subsequent involvement of breakdown products of complement, platelets, and polymorphonuclear leukocytes, and development of vasculitis; serum sickness and nephritis is common.

G 3 Signs and Symptoms and Management of Acute Anaphylaxis

Anaphylaxis is an acute and potentially lethal multi-system allergic reaction in which some or all of the following signs and symptoms occur:

- Diffuse erythema
- Pruritus
- Urticaria and/or angioedema
- Bronchospasm
- Laryngeal edema
- Hypotension
- Cardiac arrhythmias
- Feeling of impending doom
- Unconsciousness
- Shock

Other earlier or concomitant signs and symptoms can include:

- Itchy nose, eyes, pharynx, genitalia, palms, and soles
- Rhinorrhea
- Change in voice
- Metallic taste
- Nausea, vomiting, diarrhea, abdominal cramps and bloating
- Lightheadedness

- Headache
- Uterine cramps
- Generalized warmth

G 4 Management of Acute Anaphylaxis

Immediate intervention

1. Assessment of airway, breathing, circulation, and adequacy of mentation
2. Administer epinephrine intramuscularly every 5-15 minutes, in appropriate doses, as necessary, depending on the presenting signs and symptoms of anaphylaxis, to control signs and symptoms and prevent progression to more severe symptoms such as respiratory distress, hypotension, shock and unconsciousness.

Possibly appropriate, subsequent measures depending on response to epinephrine

- (a) Place subject in recumbent position and elevate lower extremities.
- (b) Establish and maintain airway.
- (c) Administer oxygen.
- (d) Establish venous access.
- (e) Normal saline IV for fluid replacement.

Specific measures to consider after epinephrine injections, where appropriate

- (a) Consider epinephrine infusion.
- (b) Consider H1 and H2 antihistamines.
- (c) Consider nebulized β_2 agonist [eg, albuterol (salbutamol)] for bronchospasm resistant to epinephrine.
- (d) Consider systemic corticosteroids.
- (e) Consider vasopressor (e.g. dopamine).
- (f) Consider glucagon for subject taking b-blocker.
- (g) Consider atropine for symptomatic bradycardia.
- (h) Consider transportation to an emergency department or an intensive care facility.
- (i) For cardiopulmonary arrest during anaphylaxis, high-dose epinephrine and prolonged resuscitation efforts are encouraged, if necessary.

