3.3.2 Adverse events – general

Adverse events (AEs) experienced by any subject at any time during the entire study will be coded using the latest version of the Medical Dictionary for Regulatory Activities (MedDRA).

AEs will be categorised for analysis according to their onset date into the following study periods:

- AEs occurring during screening/run-in period: date of Visit 1 \leq AE onset date < date of first dose of IP
- AEs occurring during on-treatment period: date of first dose of IP \leq AE onset date \leq minimum (date of last dose of IP + 33 days, date of death, date of study withdrawal)
- AEs occurring during post-treatment period (for subjects still being followed up then): date of last dose of IP + 33 days < AE onset date \leq study completion or withdrawal date
- AEs occurring during on-study period: date of first dose of IP \leq AE onset date \leq study completion or withdrawal date.

In the above, note that for subjects entering the extension study, the study completion date will be the day of enrolment in the extension study.

If the AE has a completely missing (and unresolvable) onset date, then the AE will be assumed to have occurred during the on-treatment period, unless the end date indicates unambiguously that the AE resolved before treatment started.

If the AE has a partially missing (and unresolvable) onset date, then the AE will also be assumed to have occurred during the on-treatment period, unless either the end date indicates

unambiguously that the AE resolved before treatment started, or the partial onset date is in the month/year prior to start of treatment.

Exposure adjusted incidence rates will be defined as the number of subjects reporting adverse events divided by extent of exposure for each subject, where exposure will be defined (irrespective of whether they have had the AE) as in 3.3.1 for extent of exposure for the on-treatment summaries.

Study adjusted incidence rates will be defined as the number of subjects reporting adverse events divided by duration of the on-study period for each subject as defined in [Section 3.1.2](#).

The total time at risk (years) for a treatment group will be derived as the sum of the individual subject times at risk (days) for that treatment group and divided by 365.25.

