4.2.8.1 Adverse events

AEs will be summarised separately for the on-treatment and on-study periods as defined in [Section 3.1.4](#) unless stated otherwise. All AE summaries will be presented by treatment group. AEs occurring during the screening/run-in period, or occurring post-treatment will be listed, but not summarised separately.

An overall summary table will be produced showing the number and percentage of subjects with at least one AE in each of the following categories: any AEs, serious adverse events (SAEs), AEs with a fatal outcome, AEs leading to discontinuation of IP (DAEs), and adverse events of special interest (AESIs). The total number of AEs in the different AE categories will also be presented as well as the number of subjects (i.e. accounting for multiple occurrences of the same event in a subject).

All AEs will be summarised by system organ class (SOC) and preferred term (PT) assigned to the event using the MedDRA dictionary. For each PT, the number and percentage of subjects reporting at least one occurrence of the event will be presented (i.e. subjects with multiple occurrences of the same PT will only be counted once).

Similar summaries by SOC and PT will also be presented for:

- SAEs
- Fatal AEs
- DAEs
- DAEs causally related to IP
- SAEs leading to discontinuation of IP

- Each AESI category separately
- The most common AEs (defined as those occurring in >3% of subjects in either treatment group) – by PT only

All AEs (by PT) will be summarised additionally by causality and maximum intensity. If a subject reports multiple occurrences within each SOC and PT, the maximum intensity will be taken as the highest recorded (the order being mild, moderate and severe) respectively.

In addition, each AESI category will be summarised by causality.

The AESI of injection site reactions will be further summarised by:

- Site of injection (arm, thigh, abdominal wall)
- Total number of doses administered (1, 2, ..., 13), irrespective of timing of the injection site reaction event.

Exposure-adjusted AE summaries will be presented by SOC and PT for each of the following (on-treatment summaries only):

- All AEs
- Each AESI separately

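### The SAP counts the immune complex disease AESI by one preferred term, narrower than the protocol's description, so cases recorded under a specific diagnosis can go uncounted

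*SAP*

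**What the plan says.** Protocol 8.3.8 makes immune complex disease, glossed as type III hypersensitivity reactions, an adverse event of special interest. Protocol Appendix G 2, under the title "Clinical Criteria for Defining Anaphylaxis and Immune Complex Disease", describes it as deposition of immune complexes with "development of vasculitis; serum sickness and nephritis is common".

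The SAP sets the counting rule in 8.1.2: "Immune complex disease will be defined using a single PT of" a single quoted term, "Type III immune complex mediated reaction". The same paragraph says that the general SOC/PT tables already cover this AESI, so it needs no tables of its own. SAP 4.2.8.1 lists, among the SOC/PT summaries to be produced, "Each AESI category separately". It also provides an AESI row in the overall summary table, a causality summary for each AESI category and exposure-adjusted rates for each AESI.

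On recording, protocol 8.3.6 tells sites that "the recording of diagnoses is preferred (when possible) to recording a list of signs and symptoms". SAP 3.3.2 has events coded in MedDRA.

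**The concern.** The protocol names a disease category and describes it by its manifestations. The SAP counts only a generic term for the mechanism. Sites are asked to enter diagnoses, so an investigator who diagnoses serum sickness may well enter serum sickness and not the type III mechanism behind it. Nothing in 8.1.2 would bring that event back into the AESI.

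At stake is how this safety category reads in the report. Protocol 9.4.4 says that AESIs will be summarised by treatment group, and a reader will take the AESI count as the trial's evidence on immune complex disease. The protocol treats the condition as relevant to biologics: exclusion criterion 18 bars patients with documented immune complex disease after any biologic. SAP 4.2.9.2 also allows ADA status to be examined against adverse events, and an immune-complex grouping would be useful there.

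**Working it through.** The documents give no figure for this AESI and no calculation settles the point. The check is a comparison of sections.

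**1. Protocol description against SAP rule.** Appendix G 2 names vasculitis, serum sickness and nephritis. SAP 8.1.2 names one PT, which is none of these. Under the rule as written, an event counts only if its coded PT equals that term, so an event coded to any other PT adds 0.

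**2. This AESI against the others in SAP 8.1.**

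| AESI | How cases are found |
|---|---|
| Anaphylaxis (8.1.1) | Modified SMQ with timing limits, then medical review |
| Immune complex disease (8.1.2) | One PT |
| Malignancy (8.1.3) | SMQ |
| Helminth infection (8.1.4) | Dedicated eCRF page |
| Severe infection (8.1.5) | eCRF category plus criteria |
| Injection site reaction (8.1.6) | eCRF category |
| Opportunistic infection (8.1.7) | PT list |
| Guillain-Barre syndrome (8.1.8) | SMQ |

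Immune complex disease is the only one resting on a single term.

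**3. Is the definition still open?** Sections 8.1.1, 8.1.3, 8.1.7 and 8.1.8 each say that detailed term definitions will be settled before the primary database lock. Section 8.1.2 does not, so the single-term rule is final as written.

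**4. Following one case through.** Suppose a tezepelumab subject has serum sickness, the site enters that diagnosis, and it codes to a PT other than the one in 8.1.2.
- General SOC/PT table: counted, by arm, under its own PT.
- SAE or DAE tables: counted if it qualifies.
- AESI row of the overall table: not counted as immune complex disease.
- Any exposure-adjusted rate or causality summary for this AESI: not counted.

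The event is reported but is not identified or grouped as immune complex disease.

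**5. Limits of the check.** The documents do not reproduce the MedDRA hierarchy, so step 4 assumes that serum sickness codes to a different PT from the generic one. Vasculitis and nephritis are weaker examples, because either can occur without an immune-complex mechanism and would then not be this AESI.

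**The case against.** The strongest reply is that nothing is lost. SAP 4.2.8.1 presents all AE summaries by treatment group and by SOC and PT, so each manifestation can be compared between arms under its own term. That stands: a reader might infer that such events are hidden or not compared by arm, and the SAP does not support this. Only the grouping is missing.

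Second, Appendix G 2 describes a disease process. It is not a list of qualifying diagnoses, and adding every vasculitis and nephritis PT would over-count. This also stands, and it is why a term list needs medical review behind it. It does not rescue the single PT, because serum sickness remains a clear gap.

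Third, a reader might infer that the AESI count will be close to zero by construction. That is not shown. An event reported as a type III or immune complex reaction can code to the named PT, and a low count could also reflect a rare condition.

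Fourth, it is tempting to put a number on the loss. With zero events in about 530 subjects, the rule of three gives 3/530 = 0.57% as an upper 95% bound. Dividing by a capture fraction c gives a bound on true incidence, but no document supplies c. As c runs from 1 towards 0, the result runs from 0.57% upwards without limit, so it shows only the value chosen for c. The plan sets no such bound, since AESIs are descriptive under protocol 9.4.4.

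Fifth, a reader might take the missing separate table as an error in its own right, set against the list in SAP 4.2.8.1. It is better read as a reasoned exception. For an AESI of one PT, the counts, causality and exposure-adjusted rates already appear at PT level in the general tables. The exception holds only while the definition is one PT, so it follows from the definition and needs revising with it.

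**Conclusion.** The point holds in a limited form. SAP 8.1.2 defines this AESI more narrowly than the protocol describes it and more narrowly than the SAP defines any other AESI. It provides no step to retrieve a case entered under a specific diagnosis. The AESI count and its rates are therefore liable to be too low.

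The size of the shortfall is unknown and cannot be derived from the documents. The conclusion rests on two assumptions: that some cases would be entered under the specific diagnosis, which the recording preference in protocol 8.3.6 makes plausible, and that serum sickness codes to a PT other than the named one.

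The effect is confined to how one safety category is grouped and reported. Sample size, efficacy estimates and type I error are untouched. The change should be made, because the AESI is named in the protocol and the remedy is cheap.

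**What to change.** Before primary database lock:

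- Replace the single PT in SAP 8.1.2 with a pre-specified candidate list: the generic PT, the serum sickness terms, and the vasculitis and nephritis terms.
- Confirm cases by medical review on the model of 8.1.1, so that vasculitis or nephritis without an immune-complex mechanism is not counted. Section 8.1.1 does not say that its review is blinded; doing this one before unblinding would be preferable and should be written down.
- Tabulate the confirmed AESI by arm as SAP 4.2.8.1 provides, and delete the sentence in 8.1.2 that dispenses with separate tables.

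The cost is a short term list, a small review and one extra table.

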8.1.3 Malignancy

Malignancy will be defined on the basis of an SMQ.

AESIs and related definitions based on MedDRA terms are not included in this SAP to facilitate their maintenance (e.g. management of MedDRA version changes), and for convenience in using them directly in SAS programming. These detailed definitions will be finalised by the study team prior to the primary database lock and provided together with the study datasets at the time of submission.

8.1.4 Helminth infections

Helminth infection will use an investigator-driven definition, i.e. will be directly determined from what is entered on the eCRF.

A subject will be considered to have this AESI if the subject has at least one preferred term where the dedicated Helminth Infection eCRF page was also completed for that event (linked by AE number), with AE onset date during the relevant study period for analysis.

8.1.5 Severe infections (as defined in the protocol)

Severe infections will use an investigator-driven definition, i.e. will be directly determined from what is entered on the eCRF.

A subject will be considered to have this AESI if the subject has at least one preferred term with AE onset date during the relevant study period for analysis, which satisfies the following:

- “AE Category” on Adverse Events eCRF page marked as “Severe Infection”, and one or more of the following:
 - AE is serious (“Serious” on Adverse Events eCRF page marked as “Yes”), or
 - AE required treatment with antiviral medications, intravenous antibiotics or medications for Helminth parasitic infection, or
 - AE resulted in permanent discontinuation of study drug (“Action taken, investigational product” on Adverse Events eCRF page marked as “Drug permanently discontinued”).

